Clinical Development

Clinical Trial Protocol ID: IRB_00138483

IMPROVING HEALTH INSURANCE LITERACY AMONG UTAH'S HISPANIC COMMUNITY

Principal or Coordinating Investigator: [name]

Site Name	Investigator	Staff Name(s)
		[name]
University of Utah/Huntsman Cancer Institute	[name]	[name] [name]
		[name]
		[name]
Site Name	Investigator	Staff Name(s)
Utah Health Policy Project	[name]	[name] [name] [name] [name] [name]

Document type: Draft Protocol Summary

Version number: v3

Release date: 10.4.23

Table of Contents

Clinical Development	1
Protocol Synopsis	3
Amendments	6
1. Background and Introduction	7
2. Purpose and Objectives	8
3. Study Population	9
3.1 Inclusion Criteria:	9
3.2 Exclusion Criteria:	9
4. Study design	10
5. Study Procedures	10
5.1 Recruitment/Participant Identification Process	10
5.1.1 Enrollment Goals	10
5.1.2. Process	10
5.2 Informed Consent	11
5.3 Study duration	11
5.4 Randomization	11
5.5 Procedures	11
6. Data Collection	11
7. Risks and Benefits	12
8. Cost and Compensation	13
9. Statistical Methods, Data Analysis and Interpretation	13
9.1 Aim 2	14
9.2 Aim 3	15
References	14

Protocol Synopsis

Protocol number	00138483
Title	IMPROVING HEALTH INSURANCE LITERACY AMONG UTAH'S HISPANIC COMMUNITY
Sponsor and Clinical Phase	The National Center for Advancing Translational Sciences of the National Institutes of Health, Award Number(s) UL1TR002538
Study type	
Primary Objective(s)	
We conducted with the purpose of gaining feedback on an existing health insurance education program (HIEP), originally created for young adult cancer patients. We will do this by the following study aims:
 
Aim 2. Pilot test the HIEP with Hispanic community members to further refine the intervention and evaluate its efficacy.

Study design	
Non-Experimental and/or Descriptive Research Design
 
 • Survey/Questionnaire Research 
Experimental and/or Interventional Research Design
 
 • Prospective social/ Behavioral Intervention or Experiment
Population	Hispanic community members
Inclusion criteria	
 -18-64 years of age -Self-identify as Hispanic -Speak English and or Spanish -Resident of Utah -Primary policyholder -Recently enrolled in any kind of health insurance within the past year
Exclusion criteria	
 - Younger than 18 years of age Hispanic Community Members: 
 - Not Hispanic or Latinx in origin Key Informants: 
 - Work for an organization that does not serve the Hispanic or Latinx community

Data analysis

Analysis of the pre-post health literacy survey results: McNemar's tests will identify significant changes in the percent of questions answered correctly. We will utilize logistic regression models with generalized estimating equations to calculate the odds of improvement in health insurance literacy while accounting for within-person clustering. Models will control for acculturation and/or preferred language, current insurance status, sex, and age. We will stratify models to obtain group-specific effect estimates by current insurance status, sex, 10-year age groups, and employment status.

Amendment 4

The amendment was necessary to remove personnel off the IRB who were no longer part of the team. The following sections reflected this change:

1. Contact and title - Study introduction
2. Study Location and Sponsors
3. Study information - consent process
4. Resources and Responsibilities

Amendment 3

We submitted the translated (Spanish) version of approved documents: this includes submitting the consent, baseline, follow up survey, and outline of the education pilot program. We also added new study personnel. The following sections reflect this change

1. Documents and attachments
2. Section 2: Study Location & Sponsors

Amendment 2

Amendment 2 was necessary because we needed to add new study personnel. We also needed to change the inclusion criteria to be more specific to our target population for aim 2 and to increase recruitment efforts, we also included social media as a form of recruitment. The consent form also needed to be submitted for this aim. For quality purposed, we decided to also include for the pilot sessions to be recorded. Participate compensation for aim 2 was decreased. Funding for the project ended and we needed to remove the sponsor from the study. We also increased the timeframe of the study since more time is needed to complete the study. The following sections reflect this change:

1. Study location and sponsors (Section 1, section 3)
2. Participants (section 5)
3. Study information (section 3, section 4a, section 4b, and section 6)
4. Consent process (Section 1)
5. Risk and Benefits (Section 4a and section 4c)
6. Data Monitoring Plan (Section 5)
7. Resources & Responsibilities (Section 1)
8. Documents and Attachments

Amendment 1

Translation of approved study documents needed to be submitted since a substantial portion of participants will be Spanish speaking.

1. Study information - Consent Process, Documents and attachments.

1. Background and Introduction

The 2010 Patient Protection and Affordable Care Act (ACA) increased health insurance coverage nationally by providing subsidies to lower insurance costs and expanding Medicaid. Through the ACA, funding was earmarked for health insurance navigators at community organizations to assist uninsured individuals in enrolling for coverage through the Health Insurance Marketplaces and Medicaid. In Utah, the **Utah Health Policy Project (UHPP)** is a trusted community resource, focused on advancing sustainable health care solutions for underserved Utahns through better access, education, and public policy. UHPP frequently works with the Hispanic community, who comprise 80% of the clients they serve. UHPP enrollment efforts have been stymied in recent years due to federal budget cuts that defunded health insurance navigators and the lack of state resources available to replenish cuts to the health insurance navigator program.

The goal of our CCTS project is to create materials to improve health insurance literacy for UHPP's Hispanic clients. Health insurance literacy is one's ability to make informed decisions about choosing and using health insurance. By providing Hispanic community members with resources to improve their understanding of insurance, this effort can help to address the gaps in navigation services and allow them to make informed decisions about selecting and using their insurance coverage. In this grant, we will adapt materials for Hispanic community members from [name] existing health insurance literacy program that was designed for cancer patients (NCI R01 1R01CA242729). The content of the current literacy program includes information on insurance types (e.g., public vs. private), information on insurance cost sharing mechanisms (e.g., deductibles), an overview of health insurance laws including the ACA, and cost reduction strategies (e.g., understanding in- vs. out-of-network providers). *However, the current program was not designed for a general population audience nor considering the cultural or linguistic needs of the Hispanic community.* Thus, during the CCTS grant, we will adapt and pilot test the revised program with Hispanic community members recruited by the UHPP.

2. Purpose and Objectives

The purpose of this study is to adapt a health insurance education program to the Hispanic/Latinx population Utah's population.

Aim 2. Pilot test the HIEP with Hispanic community members to further refine the intervention and evaluate its efficacy. We will then refine the intervention by pilot testing the adapted intervention with Hispanic community members (n=10-15) recruited by UHPP. Pilot testing of the HIEP will be conducted to identify acceptability of content and potential implementation issue areas, as well as any discordance in cultural values, beliefs, or feelings about health insurance.

3. Study Population

Age of Participants: 18-64 years old

Sample Size: All Centers: 75

3.1 Inclusion Criteria:

- 18-64 years of age
- Self-identify as Hispanic
- Speak English and or Spanish
- Resident of Utah
- Primary policyholder
- Recently enrolled in any kind of health insurance within the past year

3.2 Exclusion Criteria:

- Younger than 18 years of age

Hispanic Community Members:

- Not Hispanic or Latinx in origin

4. Study design

Non-Experimental and/or Descriptive Research Design:

- Survey/Questionnaire Research

Experimental and/or Interventional Research Design:

- Prospective social/behavioral intervention or experiment

5. Study Procedures

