5.1 Recruitment/Participant Identification Process

5.1.1 Enrollment Goals

Aim 2. Pilot test the HIEP with Hispanic community members to further refine the intervention and evaluate its efficacy.

- Hispanic community members (n=10-15)

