5.1.2. Process

- Prior to the beginning of recruitment for the interviews with Hispanic community members, the [name] Team and UHPP staff will work together to develop a culturally tailored survey in English and Spanish (which will be submitted for approval via an amendment). All documents will be translated from English to Spanish and submitted for IRB approval prior to recruitment of any participants. Participants will be identified through the recruitment methods outlined above.

Aim 2

- Once the intervention is adapted we will again work with UHPP to recruit additional new Hispanic community members to pilot test the intervention. Pilot testing will be conducted primarily by UHPP staff. Prior to the start of the pilot test, participants will be asked to consent using a consent cover letter. The pilot session will be recorded through Zoom or audio recorded with team recorders for fidelity purposes. Pilot testing will include a short pre-post survey to assess change in health insurance literacy. The post survey may also include a short audio recorded interview about the intervention and areas of improvement. Pilot activities will primarily be conducted by UHPP staff but may be conducted a member of the [name] team.
- Further refinement of the intervention materials and statistical analyses will be conducted by the [name] Team, again contextualized by UHPP.
- Feedback on the results of each phase of the study will be elicited from UHPP staff. The [name] team will then lead manuscript writing for each aspect of the study with assistance from UHPP. All members of the UHPP team mentioned above have been trained in Human Subjects

Research jointly by CCTS and the IRB and are present on this application.

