- The potential risks to participants are minimal. Participants may feel slight psychological distress when answering questions about health insurance and cost concerns.
- There is also a risk of breach of confidentiality of the participants.
- No direct benefit. From the societal perspective though, the benefits include improved knowledge about the Hispanic perceptions of health insurance.

8. Cost and Compensation

- There is no cost to be in this study
- There will be gift card compensation available for participants,
 - Pilot testing pre and post surveys: \$40

9. Statistical Methods, Data Analysis and Interpretation

Further refinement of the intervention materials and statistical analyses will be conducted by the [name] Team, again contextualized by UHPP.

Feedback on the results of each phase of the study will be elicited from UHPP staff. The [name] team will then lead manuscript writing for each aspect of the study with assistance from UHPP. All members of the UHPP team mentioned above have been trained in Human Subjects Research jointly by CCTS and the IRB and are present on this application.

Analysis of the pre-post health literacy survey results: McNemar's tests will identify significant changes in the percent of questions answered correctly before and after intervention. We examine differences in Health Insurance Literacy Measure before and after intervention. We will stratify this variable by age and language spoken.

References

2. Kem C. Gardner Policy Institute. *U.S. Census Bureau Estimates for Race and Hispanic Origin, Vintage 2019*. University of Utah David Eccles School of Business Kem C. Gardner Policy Institute;2020.
4. Foundation KF. Uninsured Rates for the Nonelderly by Race/Ethnicity. 2019; <https://www.kff.org/uninsured/state-indicator/nonelderly-uninsured-rate-by-raceethnicity/?currentTimeframe=0&sortModel=%7B%22colId%22:%22Black%22,%22sort%22:%22desc%22%7D>. Accessed 11/11/2020.
5. Obama B. United States Health Care Reform: Progress to Date and Next Steps. *JAMA : the journal of the American Medical Association*. 2016;316(5):525-532.

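### The Synopsis and Section 9 plan different analyses of the same pre-post survey; the Synopsis version splits adjusted GEE models of a 10-15 person pilot into strata of about 2-7 people

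*Combined protocol and SAP*

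**What the plan says.** Two current texts describe the analysis of the pilot survey.

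- **Protocol Synopsis, Data analysis.** McNemar's tests, then "logistic regression models with generalized estimating equations to calculate the odds of improvement in health insurance literacy", accounting for within-person clustering. On adjustment: "Models will control for acculturation and/or preferred language, current insurance status, sex, and age". On subgroups: "We will stratify models to obtain group-specific effect estimates by current insurance status, sex, 10-year age groups, and employment status".
- **Section 9.** McNemar's "tests will identify significant changes in the percent of questions answered correctly before and after intervention", then a before/after comparison of the Health Insurance Literacy Measure, stratified by age and language. It mentions no GEE, no covariates, and no strata by insurance status, sex or employment.

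The data come from the Aim 2 pilot. Section 5.1.2 says: "Pilot testing will include a short pre-post survey to assess change in health insurance literacy". Sections 2 and 5.1.1 both set the pilot at 10-15 people. Section 3 separately gives "Sample Size: All Centers: 75", without saying which activities that covers. Eligibility (Section 3.1) includes "Recently enrolled in any kind of health insurance within the past year", so insurance status may vary little.

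The documents do not state the number of survey questions, the GEE outcome unit, the variance estimator, a minimum stratum size, McNemar's unit of analysis, or whether subgroup results are exploratory.

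**The concern.** The two texts share McNemar's test and stratification by age, and otherwise differ in model, adjustment, outcome and strata. With no order of precedence, the analysis can be chosen after the data are seen.

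If the Synopsis is followed, its models are too large for the sample. Depending on how the outcome is defined, the stratum models either cannot be fitted or give odds ratios with standard errors that are too small. Because Aim 2 includes evaluating efficacy, a subgroup result produced this way could be read as evidence that the programme works, or does harm, in that group.

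**Working it through.** The plan contains no sample-size or precision calculation to reproduce.

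**1. Stratum sizes.** Ages 18-64 span 47 years, so at least five 10-year bands. Average per band: 10/5 = 2 to 15/5 = 3. Average per two-level factor: 10/2 = 5 to 15/2 = 7.5. Taking insurance, sex and employment as two-level gives 5 + 2 + 2 + 2 = 11 strata.

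**2. Can the age-band model be fitted?** With age dropped inside a band, four person-level coefficients remain: intercept, language (or acculturation), insurance status and sex. Three people give a person-level design of rank at most 3, which is less than 4, however many questions each answers. If insurance does not vary, three coefficients remain. Three people identify them only if they occupy three different language-by-sex cells: (4×3×2)/4³ = 24/64 = 37.5%, with both covariates split evenly.

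**3. Per-question data with default inference.** Software that drops collinear covariates still prints a pre-post odds ratio. With K people as clusters, the uncorrected sandwich error is too small by a factor of about √((K−1)/K), and the statistic behaves like t on K−1 df rather than a normal. Hence type I error ≈ P(|t(K−1)| > 1.96·√((K−1)/K)).

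| K | cut-off | approximation | simulation |
|---|---|---|---|
| 2 | 1.386 | 40% | about 35% |
| 3 | 1.600 | 25% | about 26% |
| 5 | 1.753 | 15% | 14-16% |
| 7 | 1.815 | 12% | about 12% |
| 10 | 1.859 | 10% | 7-10% across n=10-15 |
| 15 | 1.894 | 8% | 7-10% across n=10-15 |

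Simulation assumptions: 10 questions, zero mean change, person SD 1, SD of change 0.5 logit, question SD 0.5, baseline 50% or 70% correct, covariates split evenly, ages uniform. A second simulation with person SD 0.8 gave similar stratum rates, and 8-11% for the full sample with 3-4 covariates.

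**4. Any stratum significant.** These are time-only models in every stratum with two or more people, under the same assumptions. At least one of 11 strata has p<0.05 in about 80% of null studies at n=10-15, and in 69-84% over 5-20 questions with or without the insurance strata. With a Mancl-DeRouen covariance and t(K−1), error per stratum is about 3-4% and the any-stratum rate about 21-25%. Most of the excess therefore comes from the variance default and the rest from multiplicity.

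**5. One yes/no per person per visit.** Four-covariate models in strata of five fail (rank-deficient or no finite estimate) in 92-99% of runs. The full-sample adjusted model fails in 27-45% at n=10 and 4-11% at n=15.

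**6. McNemar per question, exact test.** 5-0 gives 2×0.5⁵ = 0.0625 and 6-0 gives 2×0.5⁶ = 0.031. 7-1 gives 2×(1+8)/256 = 0.070 and 8-1 gives 2×(1+9)/512 = 0.039. At least six discordant answers are needed for p<0.05. Power for a rise from 50% to 78% correct (person SD 1) is 7% at n=10, 12% at n=12 and 21% at n=15. Pooling all person-question pairs ignores clustering: type I error is 6-11% over 5-20 questions.

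**7. If 75 were the pilot size.** The default full-sample adjusted model has type I error of 5.6-5.8%. At least one of 11 strata is significant in 45-50% of null studies, and in 32-37% with the correction.

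**The case against.** The strongest reply is that the stratified GEE may never be run. Section 9 is the dedicated statistics section and omits it, and the file is labelled a draft summary. The contents page lists subsections 9.1 and 9.2 that the body lacks, so some of the difference may be stale or missing text. This stands. The documents do not say which text governs, so the mismatch leads this point and the error rates apply only if the Synopsis is followed.

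It is also fair that false precision rests on choices nobody has stated. A reader might infer that the pilot will report a spurious subgroup effect four times in five. The documents do not support that. They name no outcome unit, software or standard error, and they promise group-specific estimates rather than subgroup tests at 0.05. With one yes/no per visit, the usual problem is no estimate at all.

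Three other strong readings also fail:

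- **Bands that cannot be fitted.** At most floor(10/4) = 2 bands (n=10) or floor(15/4) = 3 (n=15) can hold four or more people. That does not prove the remaining bands unfittable, because some may be empty.
- **McNemar.** Significance does not require every discordant answer to go one way, as 8-1 shows.
- **The figure of 75.** It need not contradict 10-15, because the protocol also describes interviews, studio sessions and key informants.

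Finally, corrected intervals restore roughly nominal error per stratum, so removing every subgroup interval is partly a preference. That holds for two-level factors. With two or three people a corrected interval is too wide to use: (K/(K−1))·t(K−1)/1.96 is about 13.0 at K=2 and 3.3 at K=3, against 1.8 at K=5 and 1.5 at K=7.

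**Conclusion.** The point holds in a conditional form and should be fixed. Three parts need no simulation: the two texts differ, no precedence is stated, and the Synopsis strata average 2-3 or 5-7.5 people. An occupied age band of three or fewer cannot support the specified adjustment if language, insurance and sex all vary.

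The size of the false precision depends on per-question data, an uncorrected sandwich error, a normal reference and about 10 questions. The about-80% any-stratum figure also assumes 11 strata, time-only models and each p-value read at 0.05. Under the other outcome definition the defect is non-estimability. The stratified plan is unsuitable on either reading, but the documents do not show which failure would occur.

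**What to change.** Put one analysis text in both the Synopsis and Section 9.

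1. Report subgroup before/after results descriptively, without tests, merging small cells so that individuals cannot be identified (Section 7 lists breach of confidentiality as a risk). If an interval is kept for a larger two-level factor, use a small-sample correction and label it exploratory.
2. State the GEE outcome unit. For a full-sample per-question model, use people as clusters, a small-sample-corrected covariance (for example Mancl-DeRouen) and a t(n−1) reference. If the outcome is one yes/no per visit, drop the covariate adjustment.
3. If McNemar's test is kept, state its unit and role: exact, per question, supportive, and not pooled over person-question pairs.
4. State whether 75 covers the pilot or all phases. If it is the pilot, the full-sample adjusted model is adequate, but subgroups should remain descriptive because 11 comparisons remain.

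The cost is wording only, with no new data. Subgroup odds ratios are given up. Full-sample intervals widen by about (n/(n−1))·t(n−1)/1.96: 1.111×2.262/1.96 = 1.28 at n=10 and 1.071×2.145/1.96 = 1.17 at n=15, that is 28% and 17%.

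### Aim 2 promises to evaluate efficacy, but the pre-post survey described, with no comparator, can estimate change and cannot attribute it to the programme

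*Combined protocol and SAP*

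**What the plan says.** The aim, "Pilot test the HIEP with Hispanic community members to further refine the intervention and evaluate its efficacy", appears in the Synopsis (Primary Objective(s)), in Section 2 and in Section 5.1.1. Nothing in these places limits efficacy to a preliminary or exploratory sense.

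Section 2 describes "pilot testing the adapted intervention with Hispanic community members (n=10-15) recruited by UHPP", and Section 5.1.1 repeats the 10-15. Section 2 then gives the pilot further purposes: whether the content is acceptable, where implementation may run into trouble, and whether anything clashes with participants' values or beliefs about insurance.

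The procedures claim less than the aim. Sections 5.1.2 and 5.5 both say "Pilot testing will include a short pre-post survey to assess change in health insurance literacy". An optional recorded interview may follow, for feedback on the intervention.

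On analysis, Section 9 says that McNemar's "tests will identify significant changes in the percent of questions answered correctly before and after intervention", adds a before/after comparison of the HILM, and stratifies by age and language. The Synopsis adds logistic models with generalized estimating equations (GEE) to "calculate the odds of improvement in health insurance literacy while accounting for within-person clustering", and continues: "We will stratify models to obtain group-specific effect estimates by current insurance status", then by sex, 10-year age group and employment status.

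One inclusion criterion matters here: "Recently enrolled in any kind of health insurance within the past year".

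**The concern.** Efficacy is a claim about cause: literacy improved because of the programme. A before/after difference in one group mixes any programme effect with everything else that moves scores between the two surveys.

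Two such influences are plausible here. The first is retesting, if people do better on questions they have already seen. The second is learning elsewhere: participants enrolled in insurance within the past year, so some may be learning by using a new plan. The interval between surveys is not stated. If the second survey follows the session at once, outside learning has little room, but retesting remains.

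The stake is how the result is reported. Manuscripts are planned for each aspect of the study. With the aim worded as it is, and no sentence limiting attribution, a before/after change could be written up as efficacy, overall and by subgroup.

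**Working it through.** **Is there a sample-size calculation to reproduce?** No. The documents give no significance level, power, effect size, variability or dropout for the 10-15, so the figure cannot be re-derived.

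**Step 1: the claim against the evidence.**

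- Claim (Synopsis, Sections 2 and 5.1.1): efficacy.
- Quantitative data (Sections 5.1.2 and 5.5): one pre-post survey.
- McNemar's tests (Synopsis, Section 9): the same people, before against after.
- HILM (Section 9): before against after, with no test named.
- GEE logistic models (Synopsis): repeated answers within a person, with no term for arm or group.
- Comparator, allocation or between-group contrast: none described in the supplied text.

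No listed analysis contrasts people who received the programme with people who did not, so none estimates a programme effect. This conclusion needs no arithmetic.

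**Step 2: precision of what the design can estimate.** For a mean change score, the 95% CI half-width in SD units of change is t(0.975, n-1)/√n.

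- n=10: 2.262/3.162 = 0.715
- n=15: 2.145/3.873 = 0.554
- n=75 (the study-wide figure in Section 3): 1.993/8.660 = 0.230

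More participants narrow the interval. They do not supply a comparator.

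**Step 3: an illustration, on assumptions that are not in the plan.** Suppose the programme does nothing and other influences shift a mean score by d SD of change. Assume a two-sided paired t-test at 5%, normally distributed change scores and no dropout. The probability that the 95% CI excludes zero comes from the noncentral t distribution with noncentrality d√n.

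| Assumed d | n=10 | n=15 | n=75 |
|---|---|---|---|
| 0.2 | 8.8% | 11.2% | 40% |
| 0.5 | 29.3% | 43.8% | 99% |
| 0.8 | 61.6% | 82.1% | nearly 100% |

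The useful feature is the direction: the probability rises with n, so a larger pilot would detect a non-programme shift more reliably.

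**Step 4: limit of that illustration.** No section names a paired t-test. The named test is McNemar's, which applies to a single right/wrong question. Take a question that 30% come to answer correctly and 5% come to answer wrongly (assumed). The mean change is 0.30 - 0.05 = 0.25, the variance is 0.35 - 0.25² = 0.2875, and the SD is 0.536, so the shift is 0.25/0.536 = 0.47 SD. The exact McNemar test at two-sided 5% then shows significant improvement in about 4% of pilots at n=10 and 17% at n=15. A paired t-test at 0.5 SD gives 29% and 44%. The table in Step 3 therefore does not describe the per-question tests.

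**The case against.** The strongest reply is that this is one phrase, copied into three places of a minimal-risk pilot. The study's stated purpose is adaptation. Section 2 follows the aim with acceptability and implementation, the procedures speak only of change, and Section 9 speaks of differences before and after. The Synopsis's odds of improvement can be read literally as pre-post change, and effect estimate is ordinary regression vocabulary. No section sets an efficacy threshold or says that a change will be credited to the programme.

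Much of this stands, and it makes the overstatement moderate. It does not remove it: efficacy is part of the stated primary objective, it is unqualified, and no sentence limits attribution.

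A reader might go further in four ways that the documents do not support.

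- *The pilot should have had a control group or more people.* An uncontrolled pilot is a legitimate choice for the purposes in Section 2, and size is not the central problem.
- *The percentages in Step 3 are the plan's false-positive rates.* They rest on assumed shifts and a test the plan does not name. In those scenarios scores really do change, so an interval excluding zero is correct about change; only the attribution would be wrong.
- *It is established that there is no control arm.* The contents list has an entry 5.4 Randomization, but the supplied text runs from 5.3 to 5.5. Entries 9.1 and 9.2 likewise have no matching text. The list may be out of date or text may be missing. What can be said is that no comparator is described and no planned analysis uses one.
- *The sample is really 75.* Section 3 gives 75 without dividing it by activity, while both statements specific to Aim 2 give 10-15. Neither number changes the conclusion.

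**Conclusion.** The point holds. The pilot as described can estimate change in health insurance literacy and can inform refinement of the programme, but it cannot evaluate efficacy at any sample size. The conclusion rests on the design in the supplied text and on none of the assumed shifts. It would need revisiting only if a comparator is in fact planned.

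The change itself will be estimated loosely, with a 95% half-width of 0.72 SD of change at n=10 and 0.55 SD at n=15 for a mean score, assuming normally distributed change scores and no dropout. How large retesting or outside learning would be cannot be judged from the documents.

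The change should be made: it alters what the pilot may conclude and needs only wording. No risk to participants is at issue.

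**What to change.** 1. In the Synopsis and Sections 2 and 5.1.1, replace the efficacy phrase with: *estimate the preliminary pre-post change in health insurance literacy*.
2. In the Synopsis and Section 9, report the mean pre-post change in percent of questions correct and in HILM score, each with a 95% CI, alongside the McNemar tests.
3. Reconcile the 5.4 Randomization contents entry with the body. Provided no control arm is planned, add to Section 9: *There is no control group, so pre-post change will not be attributed to the programme.*
4. Describe the Synopsis odds of improvement and group-specific estimates, and the Section 9 results by age and language, as descriptive pre-post changes.

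As a minor clarification, state how the study-wide 75 divides by activity.

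If the percentages in Step 3 are used at all, label them as an illustration that assumes a paired t-test on a mean score and assumed shifts.

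The cost is text edits, probably submitted as an amendment, and a more modest stated aim. No participants, visits or control arm are added.
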